7.7. Close Observation

If investigational product is interrupted or discontinued as described in [Section 7.6](#), subjects should be closely monitored (contacted by the site a minimum of every 2 weeks and scheduled visits every 6 weeks; if returning to the site for a scheduled visit is not feasible, use of a local lab may be permissible at the Investigator's discretion). At a minimum, the following assessments should be conducted at each study visit:

- Physical exam and thorough review of subject reported signs and symptoms,
- Liver biochemistry (including ALP, ALT, AST, GGT, total and conjugated bilirubin, creatinine, and albumin), prothrombin time (PT)/INR, serum electrolytes, and assessment of Child Pugh (only if the subject is at the study site) and MELD scores.

In addition, a trough pharmacokinetic sample for assessment of OCA serum drug levels and its major metabolites should be obtained in any subject who develops an AE that is indicative of or consistent with hepatic injury or decompensation.

The following additional monitoring procedures should be performed for events of potential hepatic injury (per FDA Guidance for Industry on Drug Induced Liver Injury) or suspected hepatic decompensation based on criteria described in [Section 7.5.1](#), [Section 7.5.2](#), and [Section 7.5.3](#). These cases need to be discussed with the Sponsor's medical monitor:

- Repeating liver enzyme and serum bilirubin tests as described in [Section 7.5.2](#). Frequency of retesting can decrease to once a week or less if abnormalities stabilize or the study drug has been discontinued and the subject is asymptomatic, as clinically indicated.
- Obtaining a more detailed history of symptoms and prior or concurrent diseases.
- Obtaining a history of concomitant drug use (including nonprescription medications and herbal and dietary supplement preparations), alcohol use, recreational drug use, and special diets is important. Concomitant drugs with potential hepatotoxicity should be recorded and discontinued unless alternative therapies are not available. In the case of concomitant drugs potentially hepatotoxic, continued use of investigational product should be discussed with the Sponsor's medical monitor. The subject may be discontinued from investigational product, if clinically appropriate.
- Obtaining a history of exposure to environmental chemical agents or herbal supplements which may be associated with liver toxicity.
- Ruling out acute viral hepatitis types A, B, C, D (in those thought to have acute HBV infection), and E; autoimmune or alcoholic hepatitis; Wilson's disease, hypoxic/ischemic hepatopathy; and biliary tract disease.
- Investigators should consider testing for Hepatitis E virus (HEV) when assessing for hepatic decompensation as infection with HEV in patients with chronic liver diseases such as PBC may rapidly worsen with signs and symptoms similar to drug induce liver injury ([Kumar 2013](#))

- Obtaining additional tests to evaluate liver function, as appropriate (e.g., INR, direct bilirubin).
- Seeking hepatology consultation, if the Investigator is not a hepatologist

7.8. Criteria for Study Termination

The Sponsor reserves the right to terminate the study at any time. It is normal procedure to review the emerging clinical and safety data. As a result of such a review or a recommendation by the DMC, it may be necessary to stop the study before all events have been accrued, and when subjects are still active on the study. In addition, the Sponsor may terminate the study at an investigational site at any time (eg, poorly performing sites, as determined by the number of subjects enrolled or the quality of the study data).

The Investigator and/or Sponsor (or designee) must notify the Institutional Review Board/Independent Ethics Committee (IRB/IEC) of discontinuation of a site or the study and the reason for doing so.

Investigators will be informed by the Sponsor as to when the final study visit is to be completed, and should then schedule all subjects for the End of Study Visit. The window of time for scheduling the visit will be based on a final projection of when the requisite 127 adjudicated events will have been accrued.

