This study will be conducted at approximately 170 international study sites with experience in treating subjects with PBC. Prospective subjects will be identified primarily from the hospital and/or physician's database of subjects with PBC, or may be referred from other physicians. Subjects may self-refer to an Investigator if they become aware of the study through local, national, or international PBC subject societies, forums, and networks.

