7.6. Dose Adjustment, Interruption, and Withdrawal from Investigational Product or Study

Investigational product may be temporarily decreased (eg, from 10 mg twice weekly to 5 mg twice weekly, or from 5 mg twice weekly to 5 mg once weekly) or temporarily or permanently stopped based on tolerability concerns. Investigational product may be resumed at the maintenance dose upon resolution of gastroenteritis or worsening renal function or dehydration if there is no evidence of liver injury. For rechallenge following all other dose interruptions (see Table 7), investigational product should be initiated at a lower dose and subjects monitored more frequently with up-titration considered based on tolerability.

Adjustments, interruptions, discontinuation, and any rechallenge of investigational product should be implemented per the criteria outlined in Table 7. Subjects that discontinue investigational product are expected to continue in the study (and follow the regular visit schedule) until the end of the study, and the study will terminate at the time when the needed number of adjudicated events has accrued. If a subject reaches an outcome event, he or she should continue the regular visit schedule and continue taking investigational product as long as the subject has not met any of the criteria for mandatory interruption of investigational product outlined in Table 7, and the Investigator assesses it as safe. In general, subjects should be strongly encouraged to both stay on investigational product and remain in the study until study termination.

Table 7: Criteria for Dose Adjustment, Interruption, Discontinuation and Rechallenge

DOSE ADJUSTMENT		
Criteria	Action Taken with IP	Adjustment
Progress to cirrhosis and have CP A cirrhosis (CP score <7)	Adjust to a maximum daily dose of 10 mg (or equivalent placebo) in a blinded fashion	Not applicable. Remain at maximum daily dose of 10 mg (or equivalent placebo) for remainder of study.
Progress to CP B or C cirrhosis (CP score ≥7)	Adjust IP dose to 5 mg once weekly, then titrate to a maximum 10 mg twice weekly (at least 3 days apart).	After a minimum of 3 months, if at a lower dose, subjects may titrate to a maximum IP dose of 10 mg twice weekly per Investigator discretion.
New onset Severe Pruritus	Drug holiday or less frequent dosing	Return to original dose regimen if tolerated
DOSE INTERRUPTION		
Criteria	Action Taken with IP^a	Rechallenge^b

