8.4.3. Lost to Follow-up

If a subject fails to return to the clinic for a study visit, and the Investigator ceases to have contact with the subject, he or she will be withdrawn from the study.

A reasonable effort must be made to contact the subject and determine the reason(s) why a subject fails to return for a study visit or is lost to follow-up. This information and date of contact must be recorded in the appropriate CRF.

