9.7. Visit Procedures

9.7.1. Visit Windows

Visits should be based on Day 0 (not on the prior visit), eg, Month 3 should ideally occur 3 calendar months (± 2 weeks) following Day 0.

The visit windows are as follows:

Visit or Procedure	Visit Window and/or Interval
Screening	Screening Visit 1 interval is 3 to 8 weeks prior to Day 0. Screening Visit 2 interval is 1 to 6 weeks prior to Day 0. The visit window for Screening 2 visits allows for the repeat biochemistry tests to be collected at least two weeks after the initial biochemistry sample was collected and will ensure ample time to receive lab results. The overall Screening interval is up to 56 days, but screening procedures should not be performed during the last 7 days of the window. See Section 9.7.3 for scenario specific visit windows that may be applicable at Screening.
Day 0	This is the day of randomization. On-treatment visit scheduling should be calculated from this point going forward. (The first dose of investigational product should be taken the next day, on Day 1.)
Month 1	± 1 week (7 days)
Titration Visit – Standard Dosing Regimen	\geq Month 3
Titration Visit 1 – Modified Dosing Regimen	\geq Month 3
Titration Visit 2 – Modified Dosing Regimen	≥ 6 weeks after Titration Visit 1

Visit or Procedure	Visit Window and/or Interval
Titration Visit 3 – Modified Dosing Regimen (Child-Pugh B ONLY)	≥6 weeks after Titration Visit 2
Post-Titration Visit	1 month and 2 months (±1 week [7 days]) from date of titration
Month 3 to Month 12	±2 weeks (14 days)
Quarterly visits (Months 15 to EOS)	±2 weeks (14 days)
EOT (When subject discontinues investigational product)	As soon as possible upon study discontinuation and as near as possible to last dose taken
EOS (When subject terminates the study)	The final study visit; EOS will occur concurrent with EOT if a subject discontinues investigative product at the time the subject's participation in the study ends (eg, withdrawal of consent or study termination by the Sponsor); EOS will occur after the EOT if the subject discontinues investigative product but continues in the study.

EOS = end of study; EOT = end of treatment

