	Discontinued	Semiannual contact ^c	Telephone contact every 6 months (± 2 weeks)	Combined Visit, Completed as close as possible to last dose IP	
	Discontinued	Record review only ^c	Record review only	Combined visit Completed as close as possible to last dose IP	
Sponsor Termination	Discontinued	N/A	No additional visits except EOT/EOS	Combined visit Completed as close as possible to last dose IP	

Table 8: Early Discontinuation Scenarios (Continued)

	Investigational Product	Consent	Study Visit Status	EOT Visit ^a	EOS Visit ^a
Pregnancy	Interrupted	Retained	Regular Visit Schedule	Complete as close as possible to last dose IP	Complete at Final study visit
	Discontinued	Complete per the above scenarios - Early Termination or Treatment Discontinuation			
Lost to Follow-up	Discontinued	LTF	None	Unable to complete due to LTF status	

EOS = end of study; EOT = end of treatment; IP = investigational product

^a Refer to [Section 7.1.2](#) Schedule of Study Procedures, [Table 2](#) for all procedures and evaluations required at the End of Treatment and End of Study Visits.

^b Includes initiation of commercially available OCA.

^c Outcomes data to be discussed or collected include data related to adjudicated hepatic and cardiovascular event-related data. Additional data such as information on concurrent medical conditions, co-morbidities, relevant adverse events, and concomitant medications may be collected to help facilitate adjudication of these post-study events.

Some assessments noted below may be omitted if they have been completed within the 6 months (or the timeframe otherwise specified) and so long as safety issues do not warrant repeat testing.

Prior to the EOT/EOS Visit:

If possible to do before the visit, when scheduling the EOT/EOS visit, reiterate dosing instructions and advise the subject:

- If applicable, NOT to take investigational product on the morning of the next visit, and
- To bring the investigational product bottle(s); if applicable, s/he will dose at the clinic, and
- To fast overnight (at least 8 hours) prior to the next visit. Fasting is required prior to all study visits, but water is permitted.

During the EOT/EOS Visit:

- Perform a physical examination (including smoking and alcohol consumption habits).
- Review progression to cirrhosis algorithm
- Perform assessments for calculation of Child-Pugh Score.
- Assess and record vital signs (height, weight, temperature, sitting heart rate, respiratory rate, and sitting blood pressure).

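### Subjects who lose contact are withdrawn and censored with no search for death or transplant, and the protocol provides no follow-up for randomised subjects at a site closed for low enrolment

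*Protocol*

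**What the plan says.** The protocol's general rule is retention. Section 7.6 states: "Subjects that discontinue investigational product are expected to continue in the study (and follow the regular visit schedule) until the end of the study". Sections 8.4, 8.4.1, 9.7.15 and 13.1.9 repeat it. For subjects who want less involvement, Section 8.4.1 and Table 8 (Section 9.7.15) offer six-monthly telephone contact or record review, in each case as a modified consent.

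Two provisions cut across that rule without any withdrawal of consent.

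- **Lost contact.** Section 8.4.3: "If a subject fails to return to the clinic for a study visit, and the Investigator ceases to have contact with the subject", then "he or she will be withdrawn from the study". Sections 8.4.3 and 8.4.4 ask for a reasonable effort to reach the subject and record the reason. Table 8 lists the visit status of such a subject as none.
- **Site closure.** Section 7.8 says that the Sponsor "may terminate the study at an investigational site at any time (eg, poorly performing sites, as determined by the number of subjects enrolled"; data quality is the other example. It does not say what becomes of that site's randomised subjects. The only row of Table 8 that could apply is Sponsor Termination, whose visit status is "No additional visits except EOT/EOS", with the two combined. The visit-window table in Section 9.7.1 agrees: the end-of-study visit coincides with end of treatment when participation ends, "eg, withdrawal of consent or study termination by the Sponsor".

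Section 13.1.9.1 censors event-free subjects at last contact, and Section 13.1.9 assumes missing data to be missing at random.

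**The concern.** The primary endpoint (Section 13.1.3) includes death, transplant and hepatic decompensation, and transplant or death is a key secondary endpoint (Section 13.1.4). These are also plausible reasons why a patient with advancing liver disease stops attending and cannot be reached. If so, censoring at last contact removes the subject just before, or at, an event that is never recorded. The estimate is biased if this happens at different rates or for different reasons in the two arms, and no later analysis can recover an outcome that was not collected.

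The rule is also lopsided. A subject who signs a reduced consent can be followed through records to the end, while one who goes silent, having refused nothing, is withdrawn.

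Site closure raises a different issue. Low enrolment is a sensible reason to stop recruiting at a site. It says nothing about the value of following subjects already randomised there, and in a rare disease spread over many sites most sites will enrol few subjects.

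**Working it through.** **Inputs.** Section 13.1.2: exponential survival, placebo survival 0.6 at 8 years, hazard ratio 0.60, 1:1 allocation, 4 years' accrual plus 6 years' follow-up, two-sided 5%, 80% power, 10% dropout, 127 events, 428 subjects. Section 7.1: about 170 sites. Section 13.1.12: interim analyses at 64 and 96 events with Lan-DeMets O'Brien-Fleming boundaries.

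**1. The plan's own figures reproduce.** Single-look event counts for a hazard ratio of 0.60 are 121 (Schoenfeld) and 126 (Freedman). With the two interim looks, 127 events give 81.3% power (Schoenfeld drift) or 79.7% (Freedman drift), in line with the stated 80%.

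Placebo hazard: λ = −ln(0.6)/8 = 0.0639 per year; OCA 0.6λ = 0.0383. Mean event probability over the two arms by time t:

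p(t) = ½[(1 − e^(−λt)) + (1 − e^(−0.6λt))]

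Averaged over follow-up uniform from 6 to 10 years, this is 0.3308. Then 127/0.3308 = 384 and 384/0.9 = 427, against 428 stated. So N treats the 10% dropouts as yielding no events and holds no reserve beyond them.

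**2. Size of the dropout allowance in events.** 428 × 0.10 = 42.8 subjects; 42.8 × 0.3308 = 14.2 events.

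**3. Subjects per site.** 428/170 = 2.52.

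**4. An illustration (assumed).** The documents give neither the distribution of site sizes nor a number of closures. If site counts were Poisson with mean 2.52, subjects at one-subject sites would number 170 × 2.52 × e^(−2.52) ≈ 34.5. If geometric, with probability 1/(1 + 2.52) = 0.284, they would number 170 × 0.284 × 0.716 ≈ 34.6. Take 35 subjects whose follow-up ends at year 2 or year 4 instead of year 8:

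| t (years) | p(t) | p(8) − p(t) | Events lost, 35 subjects |
|---|---|---|---|
| 2 | 0.097 | 0.235 | 8.2 |
| 4 | 0.184 | 0.148 | 5.2 |
| 8 | 0.332 | – | – |

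As a share of the allowance: 5.2/14.2 = 37% and 8.2/14.2 = 58%.

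**5. Losses on top of the 10%, at fixed calendar time.** If a further share x is lost at time t, expected events are 127 × [(1 − x) + x·p(t)/0.3308], and restoring 127 needs 428 × 127/(that number) subjects.

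| Further loss, year 2 to 4 | Events | Group-sequential power (Schoenfeld) | Subjects to restore 127 |
|---|---|---|---|
| 5% | 122–124 | 79.9–80.5% | 438–444 |
| 10% | 118–121 | 78.4–79.6% | 448–461 |

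**6. Lost contact.** No size can be computed. The documents give no expected rate of lost contact and no event rate among such subjects, so the argument here is about the rule itself.

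**The case against.** Several points on the other side stand.

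- **Section 7.8 is permissive.** A reader might infer that closing a site ends study drug and all follow-up for its subjects. The documents do not say so. Section 7.8 is silent on those subjects, and the Sponsor Termination row does not name site closure. Its entries sit under study visit status, so they rule out visits, not every form of outcome collection. What is supportable is that no continued follow-up is provided.
- **Large-scale loss is not supported.** A reader might go on to suppose that every one- or two-subject site closes. Under the same two models that is 84 to 121 subjects and about 12 to 28 events, but it means shutting 59 to 78 sites, about half of those recruiting. Nothing in the protocol suggests this.
- **The 35-subject case does not nearly exhaust the dropout allowance.** It looks so by head count (35 against 43). In events it takes 37-58%.
- **Power is largely protected.** The trial runs to 127 adjudicated events, and Section 13.1.2.1 reviews event rate, recruitment and retention quarterly, blinded, with the option to add subjects. Closure for low enrolment is mostly administrative censoring, so it carries little bias.
- **The lost-contact rule is conventional and partly mitigated.** It needs both a missed visit and loss of contact, and efforts to reach the subject are required. Under Section 12.1.9 serious adverse events within 30 days of leaving the study remain reportable, as do attributable ones learned of later. Record review is currently a consent option, and Section 9.7.2 requires a signature for a change of consent, which an unreachable subject cannot give. Section 13.1.9 also lets the DMC recommend refining the missing-data strategy.

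These points reduce the size of the issue. They do not answer the main one: followed as written, Section 8.4.3 withdraws the subjects whose censoring is most likely to be informative, with no step to learn whether they died or were transplanted.

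**Conclusion.** The concern holds in a limited form. No figure in the design is wrong. The lost-contact rule and the absence of any follow-up provision after a site closes both work against the protocol's own principle of following randomised subjects to study end.

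The bias risk is in lost contact: it may be informative for the primary endpoint and for transplant or death. Its size is unknown and depends on how many subjects go silent and why. The site-closure part mainly costs time and subjects. The 5 to 8 events rest on three assumptions: 35 subjects affected, follow-up ending at year 2 to 4 instead of year 8, and the protocol's survival model. This is an improvement worth making because it is cheap, not a threat to the trial's validity.

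**What to change.** **Section 8.4.3.** Replace withdrawal with remaining in the study as out of contact and able to return. Before each interim analysis and the final analysis, check medical records and, where consent and local law allow, vital status. Adjudication under Section 13.4 already accepts hospital records and death certificates. The consent wording may need to cover these checks in advance, since a subject out of contact cannot sign a modified consent.

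**Section 7.8.** Limit the low-enrolment ground to stopping further recruitment at the site. If a site does close, offer its randomised subjects transfer to another site, or the telephone or record-review follow-up that Table 8 already contains.

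**Table 8.** State that the Sponsor Termination row applies only to termination of the whole study.

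**Cost.** Amendment wording, some low-enrolling sites kept open for follow-up, and vital status checked three times.

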8. SELECTION AND WITHDRAWAL OF SUBJECTS

8.1. Subject Population

This study will be conducted at approximately 170 international study sites with experience in treating patients with PBC. Prospective subjects will be identified primarily from the hospital and/or physician's database of patients with PBC, or may be referred from other physicians. Patients may self-refer to an Investigator if they become aware of the study through local, national, or international PBC patient societies, forums, or networks.

8.2. Subject Inclusion Criteria

1. Definite or probable PBC diagnosis (consistent with AASLD and EASL practice guidelines; [Lindor 2009](#); [EASL 2009](#)), as demonstrated by the presence of ≥ 2 of the following 3 diagnostic factors:
 - History of elevated ALP levels for at least 6 months.
 - Positive antimitochondrial antibody (AMA) titer or if AMA negative or in low titer ($<1:80$) PBC-specific antibodies (anti-GP210 and/or anti-SP100 and/or antibodies against the major M2 components [PDC-E2, 2-oxo-glutaric acid dehydrogenase complex]).
 - Liver biopsy consistent with PBC.
2. A mean total bilirubin $>ULN$ and $\leq 5x ULN$ and/or a mean ALP $>3x ULN$
3. Age ≥ 18 years

4. Either is not taking UDCA (no UDCA dose in the past 3 months) or has been taking UDCA for at least 12 months with a stable dose for ≥ 3 months prior to Day 0.
5. Contraception: Female subjects of child-bearing potential must use ≥ 1 effective method of contraception during the study and until 30 days following the last dose of investigational product. Effective methods of contraception are considered to be those listed below:
 - Barrier method, ie, (a) condom (male or female) or (b) diaphragm, with spermicide
 - Intrauterine device (IUD)
 - Vasectomy (partner)
 - Hormonal (eg, contraceptive pill, patch, intramuscular implant or injection)
 - Abstinence, if in line with the preferred and usual lifestyle of the subject
6. Must provide written informed consent and agree to comply with the study protocol

8.3. Subject Exclusion Criteria

1. History or presence of other concomitant liver diseases including:
 - Hepatitis C virus infection
 - Active hepatitis B infection; however, subjects who have seroconverted (hepatitis B surface antigen and hepatitis B e antigen negative) may be included in this study after consultation with the Medical Monitor.
 - Primary sclerosing cholangitis
 - Alcoholic liver disease
 - Definite autoimmune liver disease or overlap hepatitis
 - Nonalcoholic steatohepatitis
 - Gilbert's Syndrome
2. Presence of clinical complications of PBC or clinically significant hepatic decompensation, including:
 - History of liver transplant, current placement on a liver transplant list, or current MELD score > 12 . Subjects who are placed on a transplant list despite a relatively early disease stage (for example per regional guidelines) may be eligible as long as they do not meet any of the other exclusion criteria.
 - Cirrhosis with complications, including history (within the past 12 months) or presence of:
 - Variceal bleed
 - Uncontrolled ascites
 - Encephalopathy

- Spontaneous bacterial peritonitis
 - Known or suspected hepatocellular carcinoma
 - Prior transjugular intrahepatic portosystemic shunt procedure
 - Hepatorenal syndrome (type I or II) or Screening (visit 1 or 2) serum creatinine >2 mg/dL (178 µmol/L)
- 3. Mean total bilirubin >5x ULN
- 4. Subjects who have undergone gastric bypass procedures (gastric lap band is acceptable) or ileal resection or plan to undergo either of these procedures.
- 5. Other medical conditions that may diminish life expectancy, including known cancers (except carcinomas *in situ* or other stable, relatively benign conditions such as chronic lymphatic leukemia).
- 6. If female: plans to become pregnant, known pregnancy or a positive urine pregnancy test (confirmed by a positive serum pregnancy test by the central laboratory), or lactating.
- 7. Known history of human immunodeficiency virus infection.
- 8. Medical conditions that may cause non-hepatic increases in ALP (eg, Paget's disease or fractures within 3 months).
- 9. Other clinically significant medical conditions that are not well controlled or for which medication needs are anticipated to change during the study.
- 10. History of alcohol abuse or other substance abuse within 1 year prior to Day 0.
- 11. Participation in another investigational product, biologic, or medical device study within 30 days prior to Screening. Participation in a previous study of OCA is allowed with 3 months washout prior to enrollment in this study.
- 12. Mental instability or incompetence, such that the validity of informed consent or ability to be compliant with the study is uncertain.
- 13. History of known or suspected clinically significant hypersensitivity to OCA or any of its components.
- 14. UDCA naïve (unless contraindicated)

